### (2) Number of subjects to be surveyed and Rationale for setting the number

Number of subjects to be surveyed: 43 subjects with acute complicated Stanford Type B aortic dissection.

Rationale for Setting:

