**(8) Items and Methods for Analysis**

- 1) All-cause Mortality Rate  
Of the number of valid subjects in each evaluation period, the percentage of subjects with reported deaths is shown and is used as a characteristic evaluation.
- 2) Serious Adverse Events  
Of the number of valid subjects in each evaluation, the percentage of subjects with reported adverse events including stroke, respiratory failure, cardiac infarction, renal failure, paraplegia/paraparesis, and bowel ischemia is shown and is used as a characteristic evaluation. Causal relationships※1 are investigated for each event.

Causal relationships※1

For each report of an adverse event, the physician in charge evaluates the primary relationship to the Device or procedure as follows.

- Not related to the Device or procedure -In case the cause or primary cause of an adverse event is due to a cause not related to the Device or procedure

- Related to the Device - The cause or primary cause of an adverse event is due to a function or characteristic of the Device
- Related to TEVAR - In case the cause or primary cause of an adverse event is due to TEVAR procedure (not due to the Device)
- Related to concomitant procedure - In case the cause or primary cause of an adverse event is due to concomitant procedure (not related to the Device or TEVAR)
- Unknown relation -Causal relationship with an adverse event cannot be determined

3) Primary Entry Tear Exclusion

Of subjects confirmed to have primary entry tear in each evaluation period, the percentage of those with primary entry tear is calculated. Confirm that primary entry tear exclusion is not significantly lower than that in TAG 08-01 study.

4) Aortic Rupture

Of the number of valid subjects in each evaluation period, the percentage of subjects with aortic rupture is shown and is used as a characteristic evaluation.

5) Primary events related to the Device

Of the number of valid subjects in each evaluation period, the percentage of subjects with a primary events related to the device※2 is shown and is used as a characteristic evaluation.

Primary events related to the device※2

Events reported as endoleak, access and deployment failure, luminal obstruction (including device compression and thrombus), stent graft structural failure, extrusion/erosion, stent graft migration, migration between components, and wire fracture, as well as selected as primary in severity.

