2.3.1 Safety Data

All-Cause Mortality (Dissection and Trauma)

All-cause mortality through 30 days post-treatment will be evaluated. For the dissection cohort, this result will be compared descriptively with the performance goal of 0.25 from the TAG 08-01 study. Additionally, Kaplan-Meier plots of all-cause mortality will be generated.

Serious Adverse Events (Dissection and Trauma)

The proportion of subjects reporting serious adverse events (including stroke, respiratory failure, myocardial Infarction, renal failure, paralysis/paraparesis and bowel ischemia) among the eligible subjects in each follow-up period shall be provided.

CONFIDENTIAL INFORMATION

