2.3.2 Efficacy Data

Primary Entry Tear Exclusion (Dissection)

The proportion of subjects reporting exclusion of the primary entry tear shall be evaluated among the eligible dissection subjects in each follow-up period. The result in the one month study window will be compared descriptively with the primary efficacy endpoint result from the TAG 08-01 study.

Aortic Rupture (Dissection and Trauma)

The proportion of subjects reporting aortic rupture among the eligible subjects in each follow-up period shall be provided.

Major Device Events (Dissection and Trauma)

The proportion of subjects reporting major device events among the eligible subjects in each follow-up period shall be provided. Major device events include endoleak, access and deployment failure, lumen obstruction (including device compression and thrombus), device integrity events, extrusion/erosion, device migration, intercomponent migration and wire fracture with severity from major A to major D selected.

Secondary Interventions (Dissection and Trauma)

The proportion of subjects reporting secondary interventions among the eligible subjects in each follow-up period shall be provided with the treatment and reason of the intervention.

True and False Lumen Diameter Changes (Dissection)

Changes in true lumen and false lumen measurements in both the treated segment and distal to the treated segment among the eligible dissection subjects in each follow-up period shall be provided. Changes of ≥ 5 mm will be considered an increase, changes of ≤ -5 mm will be considered a decrease, and changes between -5 mm and 5 mm will be considered stable.

Lesion Diameter Changes (Trauma)

Changes in lesion diameter among the eligible trauma subjects in each follow-up period shall be provided. Changes of ≥ 5 mm will be considered an increase, changes of ≤ -5 mm will be considered a decrease, and changes between -5 mm and 5 mm will be considered stable.

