2.4 Statistical Hypotheses

No formal hypothesis tests will be performed.

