4.2 Timing of Analyses

Analysis of the study results will be ongoing throughout enrollment. Serial analyses of long-term results will occur during the follow-up period. No adjustment to overall alpha level will be made for this surveillance study.

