4.3 Specified Analyses

Statistical analyses will include summary statistics, including frequency counts for categorical variables, and measures of dispersion for continuous variables.

[REDACTED] No inferential analyses will be performed.

CONFIDENTIAL INFORMATION

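### The protocol wants tear exclusion confirmed as not significantly lower than in TAG 08-01, but the SAP permits no test, and a non-significant result in at most 43 subjects would confirm little

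*Protocol*

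**What the plan says.** Protocol section (8), item 3, has two sentences on primary entry tear exclusion. The first sets the calculation: "Of subjects confirmed to have primary entry tear in each evaluation period, the percentage of those with primary entry tear is calculated". The second sets the conclusion to be reached: "Confirm that primary entry tear exclusion is not significantly lower than that in TAG 08-01 study". The other outcome items in section (8) are only to be displayed as a characteristic evaluation; this is the only one with a result to confirm.

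SAP section 2.3.2 reports the exclusion proportion in every follow-up period and then limits the external comparison: "The result in the one month study window will be compared descriptively with the primary efficacy endpoint result from the TAG 08-01 study". SAP section 2.4 states: "No formal hypothesis tests will be performed". SAP section 4.3 states: "No inferential analyses will be performed". On alpha, SAP section 4.2 says only: "No adjustment to overall alpha level will be made for this surveillance study".

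For 30-day mortality, SAP section 2.3.1 gives both the type of comparison and the figure: "For the dissection cohort, this result will be compared descriptively with the performance goal of 0.25 from the TAG 08-01 study". The visible text gives no corresponding figure for tear exclusion.

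**The concern.** There are two problems.

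- **The documents disagree.** An analyst who follows the SAP has no means of producing the protocol's confirmation. An analyst who produces it must depart from the SAP. Annual reports go to the regulator (protocol section (5)), so it matters which statement appears in them.
- **The protocol's rule is unsound if it is applied.** Failing to find a significant shortfall in a small cohort does not show that there is none. The fewer the evaluable subjects, the easier it generally is to pass.

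The claim at stake is the only effectiveness comparison with TAG 08-01 in either document, in a study whose stated purpose is to confirm effectiveness and safety.

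**Working it through.** **Step 1: the texts side by side**

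| Element | Protocol (8), item 3 | SAP |
|---|---|---|
| Type of comparison | Significance, worded as confirmation | Descriptive (2.3.2); no tests (2.4); no inference (4.3) |
| Time point | None named; the preceding sentence covers every evaluation period | One-month window (2.3.2), days 15–59 (Table 1) |
| Test and alpha | None | None; 4.2 says only that alpha is not adjusted |
| TAG 08-01 value | None visible | Primary efficacy endpoint result, no number visible |

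The contradiction follows from the first row alone and depends on no assumed number. No visible passage reconciles the two documents.

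**Step 2: what non-significance would mean**

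The only stated input is the cohort size: "Number of subjects to be surveyed: 43 subjects with acute complicated Stanford Type B aortic dissection". Its rationale is not visible, so 43 cannot be reproduced from the documents. The benchmark p0, the alpha and the evaluable n are assumed below, and the results are illustrations.

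*Fixed benchmark.* With X subjects showing exclusion out of n, the result is significantly lower if P(X ≤ x | n, p0) ≤ alpha. The lowest passing count x* is the smallest x with P(X ≤ x | n, p0) > alpha. A true deficit d passes with probability P(X ≥ x* | n, p0 − d).

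Example with p0 = 0.90, n = 43 and one-sided alpha = 0.025: P(X ≤ 34) = 0.0244, which is significant; P(X ≤ 35) = 0.0607, which is not. So x* = 35, and 35/43 = 81.4% passes. If the true rate is 0.80, P(X ≥ 35) = 0.50.

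| Assumed p0 | Lowest passing result | Exact 95% CI of that result | 10-point deficit passes | 15-point | 20-point |
|---|---|---|---|---|---|
| 0.85 | 32/43 (74.4%) | 58.8–86.5% | 61% | 33% | 13% |
| 0.90 | 35/43 (81.4%) | 66.6–91.6% | 50% | 22% | 7% |
| 0.95 | 38/43 (88.4%) | 74.9–96.1% | 36% | 11% | 3% |
| 0.98 | 40/43 (93.0%) | 80.9–98.5% | 23% | 5% | 1% |

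**Step 3: sensitivity to the assumptions**

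- *One-sided 5% instead of 2.5%, n = 43.* Only the 0.85 row changes: x* becomes 33, and a 10-point deficit passes 48% of the time and a 20-point deficit 7%.
- *35 evaluable subjects, one-sided 2.5%.* A 10-point deficit passes 76%, 60%, 57% and 38% of the time for the four benchmarks.
- *TAG 08-01 treated as a sample.* Assume 50 subjects with true rate 0.94, against 43 subjects with true rate 0.94 − 0.10 = 0.84. Summing over both binomial distributions with a one-sided Fisher test, the deficit passes 78% of the time at 2.5% and 64% at 5%.

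**Step 4: what an interval would show**

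Exact (Clopper-Pearson) two-sided 95% intervals with n = 43: 39/43 (90.7%) gives 77.9–97.4%; 41/43 (95.3%) gives 84.2–99.4%; 43/43 has lower limit 0.025^(1/43) = 0.918, or 91.8%.

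**The case against.** The strongest reply is that the harm is hypothetical. The SAP is the more specific analysis document, and it rules out testing twice. An analyst who follows it runs no test, so the pass rates describe an analysis that nobody has planned. That is fair as to the numbers: they are illustrations, and the contradiction does not need them. It does not remove the risk that a report repeats the protocol's claim of confirmation with no analysis behind it.

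Second, the protocol may mean *significantly* in the loose sense of *markedly*, since its terminology is loose elsewhere. This is possible but weak. The word stands in a section on analysis methods, and only this item departs from the standard wording of its neighbours. The loose reading would also leave the confirmation without any criterion, and the repair would be the same.

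Third, the missing TAG 08-01 value may have been redacted, and the SAP does name the comparator. This stands, so the absence is not counted as an error. The mortality comparison shows only that such a figure can be stated.

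Fourth, the SAP's one-month window may fill a gap in the protocol rather than contradict it. This largely stands: the time point is a secondary part of the mismatch.

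Finally, saying that a 10-point deficit would often pass depends on the benchmark. At 0.95 or 0.98 with all 43 subjects evaluable and a fixed benchmark, the test would detect it in most cases. This also stands, and the range has to be given whenever the point is made.

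**Conclusion.** The concern holds. The protocol asks for a conclusion based on significance, and the SAP forbids the analysis that would support it. This rests on the visible text alone. One sentence in SAP section 4.3 is redacted, but the sentence after it still excludes inference.

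As a rule, treating non-significance as confirmation is unsound at this sample size. Against a fixed benchmark with n = 43 and one-sided 2.5%, the chance of passing a true 10-point deficit runs from 23% to 61% over assumed benchmarks of 0.98 down to 0.85. It is higher with fewer evaluable subjects or if the uncertainty in TAG 08-01 is counted. Large deficits would usually be caught against a fixed benchmark with all 43 evaluable: 20 points passes between 1% and 13% of the time.

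This should be fixed, but its consequence is limited. Tear exclusion is one of five effectiveness endpoints in a single-arm surveillance study whose priority item is 30-day mortality.

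**What to change.** Replace the confirmation sentence in protocol section (8), item 3, and align SAP section 2.3.2, with wording such as:

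> *The proportion with tear exclusion at one month is presented with an exact two-sided 95% confidence interval next to the TAG 08-01 primary efficacy result. Lack of a significant difference is not treated as confirmation.*

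Then:

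- State the TAG 08-01 value in SAP section 2.3.2, as is done for mortality in 2.3.1.
- Amend SAP section 4.3 so that this interval is allowed. Section 2.4 can stay as it is.
- In the same edit, correct the preceding protocol sentence, which counts subjects with an entry tear although the endpoint is its exclusion.
- If a claim of confirmation is to be kept, set a threshold in advance and compare the lower confidence limit with it.

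The interval is the better repair but is not needed to remove the contradiction; deleting the protocol sentence would do that.

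The cost is a short protocol edit, short changes to SAP sections 2.3.2 and 4.3, and one exact interval, with no more patients or data. The downside is a result that looks less conclusive, since even 43 exclusions in 43 subjects would leave a lower limit of 91.8%.

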- Incidence rate of secondary interventional treatment (including additional implantation of the Device and conversion to surgical operation), description of the procedure, and reasons for intervention

Of the number of valid subjects in each evaluation period, the percentage of subjects with secondary interventional treatment and the details of the procedure/the reason for the intervention are shown and is used as a characteristic evaluation.

6) Change in true and false lumen diameters

Of the number of valid subjects in each evaluation period, subjects with the change in true and false lumen diameters of the treated site and the distal side of the treated site are shown and are used as a characteristic evaluation.

8) Evaluation period

Each evaluation period is as follow

Follow-up visit	Desirable period for visit (Number of days)	Evaluation period (Number of days)
Time of Operation	0	0
Time of Discharge	Before Discharge	None Specified
After Operation	1~14	1~14
1 Month	23~44	15~59
6 Months	150~210	60~242
12 Months	275~455	243~546
24 Months	640~820	547~911
36 Months	1005~1185	912~1275
48 Months	1370~1550	1276~1640
60 Months	1735~1915	1641~2006

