**(11) Other necessary items**

In case of subjects with traumatic thoracic aortic transections enrolled during this surveillance study period for acute complicated Stanford type B aortic dissection, the results are traced as follows.

Item	Contents
Number of subjects to be surveyed and rationale for settings	Number of subjects to be surveyed: No setting Rationale for setting: Due to the difficulty in estimating the number of subjects
Target Patients for Surveillance Study	Patients with traumatic thoracic aortic transections meeting all of the following requirements for descending thoracic aortic lesions. 
 
• Have adequate iliac/femoral artery access routes
 
• Inner diameter of proximal and distal aortic necks is within the range of 16-42mm
 
• ≥20mm aortic neck length without aneurysm on proximal and distal sides of the lesion
 

Number of sites by department to be surveyed	The same as the survey sites for acute complicated Stanford Type B aortic dissection
Method of Surveillance Study	Patients are enrolled and surveyed if the device is used in patients with traumatic descending thoracic aortic transections at sites that contracted for this survey after obtaining a patient with

	complicated acute Stanford Type B aortic dissection.
Scheduled Period of Surveillance Study	Enrollment period: Until the enrollment of 43 subjects with acute complicated Stanford Type B aortic dissection Observation Period: 5 years after implantation of the device
Items, etc. for Surveillance Study	The same as acute complicated Stanford Type B aortic dissection
Analytical Items and Method	All-cause mortality rate, serious adverse events, primary events related to the Devices, secondary interventional treatment and change in lesion diameter are analyzed by the same method as for acute complicated Stanford Type B aortic dissection.

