2.5 Sample Size Determination

43 subjects

The sample size of

Subjects in the trauma cohort

will be enrolled from sites already participating in the dissection cohort, and there is no sample size requirement for the trauma cohort.

CONFIDENTIAL INFORMATION

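### In the visible text, SAEs, rupture, major device events and secondary interventions are reported only window by window, so the share of patients ever affected by 1 or 5 years cannot be read from them

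*Protocol*

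**What the plan says.** Protocol section (8) summarises secondary intervention as "Of the number of valid subjects in each evaluation period, the percentage of subjects with secondary interventional treatment", and for rupture "the percentage of subjects with aortic rupture is shown and is used as a characteristic evaluation". Serious adverse events (SAEs) and device events get the same kind of summary. The Protocol names secondary intervention as an 'incidence rate' in sections (7) and (8), but the analysis it describes is a percentage per window.

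The SAP changes the denominator word from 'valid' to 'eligible' and keeps the structure. For device events, section 2.3.2 says: "The proportion of subjects reporting major device events among the eligible subjects in each follow-up period shall be provided". For reinterventions: "The proportion of subjects reporting secondary interventions among the eligible subjects in each follow-up period shall be provided". SAP 2.3.1 treats SAEs alike. Neither denominator word is defined in the visible text; SAP 4.1 says only that everyone enrolled is reported on. Nothing visible says whether a subject counted in one window may be counted again in a later one.

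The one visible cumulative method is in SAP 2.3.1: "Additionally, Kaplan-Meier plots of all-cause mortality will be generated". The general methods in SAP 4.3 read: "Statistical analyses will include summary statistics, including frequency counts for categorical variables, and measures of dispersion for continuous variables". A redacted passage follows.

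For the trauma cohort, Protocol section (11) says that several items, including "secondary interventional treatment and change in lesion diameter are analyzed by the same method" as for dissection. SAP 2.5 adds that "there is no sample size requirement for the trauma cohort".

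**The concern.** The study observes patients for 5 years to confirm effectiveness and safety. A natural summary of durability is the share of patients who needed a reintervention, or had a major device event, by 1 year and by 5 years. Percentages per window do not add up to that. Counting subjects rather than events removes repeats within a window but not across windows. A persistent endoleak or a second reintervention can put the same person in several cells, and the table would look the same if those cells held different people.

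The visible plan recognises the need for a cumulative view of mortality, where it adds Kaplan-Meier plots to the window summaries, but shows nothing similar for these four items. If the mortality method were simply extended to them with deaths censored, the result would overstate the risk, because a patient who has died can no longer have a reintervention.

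**Working it through.** **Inputs from the documents.** Dissection cohort: 43 (Protocol (2), SAP 2.5). Analysis windows in days (Protocol (8) item 8, SAP Table 1, identical): 0; 1-14; 15-59; 60-242; 243-546; 547-911; 912-1275; 1276-1640; 1641-2006. That is 9 numbered windows, of which 5 end by day 546. They are contiguous, so each dated event falls in exactly one. Day 365 lies inside 243-546 and day 1826 inside 1641-2006, so no window ends at 1 year or at 5 years.

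**Bounds on the share ever affected.** Suppose k subjects are affected in each of W windows and all 43 are in every denominator. The fewest people ever affected is k (the same people each time). The most is k × W (all different).

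| k | Each cell | Through day 546 (W = 5) | Through day 2006 (W = 9) |
|---|---|---|---|
| 1 | 1/43 = 2.3% | 1/43 to 5/43 = 2.3% to 11.6% | 1/43 to 9/43 = 2.3% to 20.9% |
| 2 | 2/43 = 4.7% | 2/43 to 10/43 = 4.7% to 23.3% | 2/43 to 18/43 = 4.7% to 41.9% |

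No event rate is predicted here; k is only an illustration. Day 0 is included because it is an analysis window and because access and deployment failures, which count as major device events, would naturally fall there. Without it the upper end for k = 1 is 8/43 = 18.6%.

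**Effect of the denominator.** Two affected subjects in the 60-month window give 2/43 = 4.7%, 2/30 = 6.7% or 2/20 = 10.0%, for assumed denominators of 43, 30 and 20.

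**How to estimate the share ever affected.** The documents give no event, death or loss rates, so the next figures rest on assumptions. With hazards h_E (first reintervention), h_D (death) and h_L (loss), and cumulative hazards H:

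- True risk by t: ∫ h_E exp(−H_E − H_D)
- First events over all enrolled: ∫ h_E exp(−H_E − H_D − H_L)
- Kaplan-Meier with death censored: 1 − exp(−H_E)

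Assumptions, with annual figures used as hazards:

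- Milder: 5% dead by day 30, then 4%/yr; first event 6% by day 60, then 4%/yr; loss 3%/yr.
- Base: 10%, then 6%/yr; 8%, then 5%/yr; loss 5%/yr.
- Harsher: 15%, then 8%/yr; 12%, then 8%/yr; loss 8%/yr.

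| Case, time | True | First events / all enrolled | Kaplan-Meier, death censored |
|---|---|---|---|
| Base, 1 year | 10.7% | 10.6% | 11.8% |
| Milder, 5 years | 20.0% | 19.0% | 22.5% |
| Base, 5 years | 22.8% | 21.1% | 27.8% |
| Harsher, 5 years | 30.7% | 27.4% | 40.2% |

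Hand check of the base Kaplan-Meier figure at day 1826: 1 − 0.92 × exp(−0.05 × 1766/365.25) = 1 − 0.92 × 0.785 = 27.8%.

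**Precision at N = 43.** In 4,000 simulated samples under the base case, the median 95% CI for reintervention was about 3% to 21% at 1 year (31 at risk) and 11% to 36% at 5 years (16 at risk). For rupture, 0 of 43 with full follow-up gives an exact upper limit of 1 − 0.025^(1/43) = 8.2%.

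**The case against.** The strongest reply is that the answer may sit in text we cannot see. A passage in SAP 4.3 is redacted exactly where further methods would stand, headings 5.1, 5.2 and 6.1 to 6.3 are blank in the contents list, and the list of tables, figures and listings under SAP 6.0 is not shown. A reader might infer that the plan contains no cumulative output and no repeat rule. The documents do not support that; they support only that none is visible. This limit stands.

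Second, the study is descriptive. SAP 2.4 and 4.3 rule out tests and inference, the priority item is 30-day mortality, and no visible sentence sets a 1- or 5-year cumulative objective for these items. This too stands: error rates and sample size are untouched, and the window percentages are not wrong. Yet the Protocol itself uses the term 'incidence rate' and follows patients for 5 years, so the cumulative share is a reasonable thing to expect.

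Third, the range is a logical extreme. Its low end needs one person to be affected in all 9 windows, which is implausible for rupture. Interventions must also be reported with treatment and reason, which in a small cohort may help to identify repeats, although display by subject is not confirmed.

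Fourth, a competing-risk estimate adds little to a plain first-event count: 21.1% against 22.8% at 5 years in the base case, well inside an interval of about 11% to 36%. Neither document proposes Kaplan-Meier for these items, so the 27.8% and 40.2% warn against one way of filling the gap and do not criticise the plan.

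**Conclusion.** The concern holds for the visible text as an improvement worth considering. Percentages by window alone leave the share ever affected undetermined: 2.3% to 20.9% for a table reading 2.3% in all 9 windows, or 2.3% to 11.6% through day 546. Those bounds assume 43 in every denominator and are the widest possible. The ambiguity matters most for secondary interventions, device events and SAEs, and little for rupture.

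The missing definitions of 'valid' and 'eligible' and the missing repeat rule are matters of detail. The substantive gain is a cumulative first-event summary. The comparison of estimators rests on assumed rates. It shows that a count over all enrolled is close to the truth at 1 year in the base case, somewhat low at 5 years in every case, and safer than Kaplan-Meier with deaths censored.

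**What to change.** First ask the sponsor whether the redacted or unseen parts of the SAP already plan a cumulative output for these items. If so, confirmation is enough.

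If not, keep the window tables and add to SAP 2.3.1 and 2.3.2, for the dissection cohort:

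- A descriptive cumulative incidence of the first event from implantation (Aalen-Johansen), reported at 1 and 5 years, for secondary intervention, any major device event and any SAE.
- Death as the competing event, with a fatal SAE counting as the event itself; loss to follow-up censored at last contact; numbers at risk shown. Do not use Kaplan-Meier with death censored.
- 95% CIs labelled descriptive, in keeping with SAP 4.3. For device events found on imaging, state that time runs to the date of detection.

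For rupture, and for the trauma cohort, report the number of subjects ever affected with an exact CI. Reconcile the documents on trauma: SAP 2.3.2 includes rupture for that cohort, whereas the analysis row in Protocol (11) does not list it.

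If event or last-contact dates are not on the forms, which the documents do not show, report the number ever affected over all enrolled instead.

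In the same edit, define 'valid' and 'eligible' in Protocol (8) and SAP 4.1, and say whether window tables count first events or any events.

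The cost is some wording and a little programming. Estimates will be imprecise at N = 43, as the intervals above show.
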